#### Premature termination of clinical trial participation:

- Patients may discontinue participation in the clinical trial at any time by revoking their informed consent.
- The Investigator may withdraw a patient at any time if it is in the best interest of the patient based upon clinical assessments.
- Patient is lost to follow-up.
- Re-transplantation. Patients who are eligible for and/or listed for re-transplantation will continue to participate in the trial until they receive re-transplantation surgery.
- Pregnancy (the patient will be followed via a pregnancy registry).
- Zambon SpA may choose to terminate the study at a site or as a whole for reasons such as, but not limited to, medical futility, safety concerns, or poor study site performance.

Patients stopping to take study treatment but not revoking their consent will be encouraged to continue the visits planned until the scheduled end and perform all the important safety and efficacy assessment for the full duration of the study.

If the patient fails to return for clinical follow-up, the patient will be contacted by telephone or a letter will be sent requesting a mandatory clinic visit and the reason for non-compliance will be documented.

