#### 10.3 Patient Withdrawal Criteria

In the event of patient withdrawal, the Investigator must complete the appropriate end of study form in the eCRF as soon as possible after withdrawal, stating the reason and date of withdrawal. An automated e-mail alert will be generated by the eCRF system and will be sent to the Clinical Research Organization (CRO).

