#### 10.3.1 Procedures for patients Withdrawal and Type and Timing of Data Collection

The patient is free to withdraw from the clinical trial for any reason and at any time without giving a reason for doing so and without penalty or prejudice. The Investigator is also free to terminate a patient's involvement in the clinical trial at any time if the patient's clinical condition warrants it and if it is in the best interest of the patient based upon clinical assessments.

If the subject decides to withdraw the consent or the Investigator decide to withdrawn a patient from the study, he/she should perform:

- End of Treatment Visit (Visit 9) PRIOR to discontinuation, whenever possible (the reason for premature withdrawal should always be documented)
- A final clinical trial visit (Visit 10) at least 1 month after Visit 9, if possible

If subjects permanently discontinue study treatment and maintain consent, or the Investigator decide to withdrawn a patient from study treatment, patients should be followed for additional outcome information. Subjects should be encouraged to continue the participation in the clinical trial until the scheduled end, regardless of the treatment arm. Subjects should perform all study visits required by Study Protocol performing all important safety and efficacy assessments for the full duration of the Study.

It is also possible that the Competent Authority(ies), IRBs/ECs or the sponsor request termination of the clinical trial, if there are concerns about conduct or safety.

Reasons for withdrawal are outlined in detail in Section 9.6.1

The reasons for withdrawal must be recorded in the eCRF.

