#### 10.3.4 Completion of Clinical Trial and Loss to Follow-up

Patients will be considered to have completed the clinical trial if they were followed-up through Study Visit 9 (Study Week 48).

A patient will be considered lost-to-follow-up only if no contact has been established by the time the clinical trial is completed such that there is insufficient information to determine the patient's status at Visit 9 (Week 48). The Investigator should document attempts to re-establish contact with any missing patient throughout the clinical trial period. If contact with a missing patient is re-established, IMP inhalation and follow-up should resume according to the protocol.

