# 9.2.4 Per Protocol Set (PPS)

The PPS is defined as all patients included in the FAS

Final Version 5.0 Page 28 of 76

- who complete randomized treatment as scheduled or who are withdrawn prematurely due to lack of efficacy or lack of tolerability of the clinical trial treatment, and
- for whom no major protocol deviations interfering with the assessment of treatment efficacy are observed.

For selected efficacy endpoints, including the primary endpoint, the PPS may be used as a supplementary analysis to assess the impact of drop-outs and major protocol deviations on the results.

Lack of efficacy is defined by the withdrawn reason "Lack of efficacy" as collected in the End Of Study CRF form. Lack of tolerability is defined by the withdrawn reason "Adverse Event (Including SAE/Death)" as collected in the End Of Study CRF form.

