#### 10 **DISPOSITION**

The number of patients screened, failed screening (patients who did not meet all eligibility criteria and was not randomized), enrolled (patients with informed consent and all eligibility criteria met or randomized), treated but not randomized, randomized (treated, and not treated with clinical trial treatment), completing clinical trial treatment (and reasons for not completing), and completing the clinical trial (and reason for not completing) will be presented in frequency tables by treatment group.

The number of patients in each analysis population (SAF, FAS, and PPS) will be summarized by treatment group. A by-patient listing of disposition will be provided.

All major protocol deviations will be presented as a frequency table by treatment group and in a by-patient listing for all randomized patients, which will include the category of the deviation, the deviation text, and whether the patient was excluded from PPS.

In addition, the counts on COVID-19 related major PDs will be provided, together with a by-patient listing for all COVID-19 related PDs.

In addition, a listing of the patients affected by Coronavirus Disease of 2019 (COVID-19) and their COVID-19 AE details will be provided for the FAS.

A table for the summary of stratification factors by treatment group for FAS and a separate listing of patients with mis-stratifications will be displayed.

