### 15.2.2 Exposure to Study treatment (SoC or SoC+L-CsA)

SoC therapy period starts at randomization date and stops at date of study completion or early termination. L-CsA treatment period starts at date of first dose of L-CsA and stops at the date of last dose administered.

Descriptive statistics for the duration of any study treatment (SoC or SoC+L-CsA) in days and weeks will be provided. Since the SoC will cover the entire study period post-randomization, the study treatment duration (SoC or SoC+L-CsA) will be calculated as the difference between the date of study completion/early termination and randomization plus 1.

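### As SAP 9.2.4 is most naturally read, the Per Protocol Set excludes L-CsA patients who stop the drug for an adverse event or lack of efficacy but stay in follow-up; no matching SoC exclusion arises

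*SAP*

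**What the plan says.** The first PPS criterion in SAP 9.2.4 admits patients "who complete randomized treatment as scheduled or who are withdrawn prematurely due to lack of efficacy or lack of tolerability of the clinical trial treatment". A second criterion requires no major deviation that interferes with the efficacy assessment. The section then fixes where the two reasons come from. Lack of efficacy is the withdrawal reason of that name, "as collected in the End Of Study CRF form. Lack of tolerability is defined by the withdrawn reason" for adverse events (serious events and death included), again on the End Of Study form. No other source is named. Protocol 15.1 has the same criterion without naming a form.

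On the form, Protocol 10.3 says that in the event of withdrawal "the Investigator must complete the appropriate end of study form in the eCRF as soon as possible after withdrawal", with the reason and date. On patients who stop treatment but keep consent, Protocol 10.3.1 says: "Subjects should be encouraged to continue the participation in the clinical trial until the scheduled end, regardless of the treatment arm". Protocol 9.6.1 makes the same request. Protocol 10.3.4 counts anyone followed through Visit 9 as having completed the trial, with no condition on drug intake.

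On treatment periods, SAP 15.2.2 ends the L-CsA period at the last dose. For the control arm, "SoC therapy period starts at randomization date and stops at date of study completion or early termination".

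SAP 10 plans to report completion of treatment and completion of the trial as two items, each with reasons for not completing. SAP 14.3.1 reruns the primary analysis on the PPS.

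**The concern.** The exemption for lack of efficacy and tolerability appears intended to stop the PPS from becoming a set of patients who did well on treatment. Reading the reason from a study-exit form ties it to leaving the study, whereas the event of interest is leaving the drug. In this trial the two are deliberately separated: stoppers are asked to stay, SAP 8.3.4 records the recommendation that they do, and SAP 14.2.1 plans an imputation model built on those who do.

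The better sites follow that instruction, the more L-CsA patients with complete FEV1 data would be removed from the PPS, while patients who stop for the same reasons and leave, with shorter data, are retained. Because only one arm has a drug that can be stopped while the patient stays, the removal is one-sided. SAP 9.2.4 gives the PPS the task of showing how drop-outs and major deviations affect the results, and a set depleted in one arm does that poorly.

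**Working it through.** The point turns on a definition, so the main check is to follow the rule through each case. In all cases, assume no major deviation.

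| Case | Completed randomized treatment? | Listed reason on End Of Study form? | In PPS? |
|---|---|---|---|
| L-CsA, stops drug for adverse event or lack of efficacy, attends to Week 48 | No (L-CsA period ends at last dose, SAP 15.2.2) | No (not withdrawn; trial completer, Protocol 10.3.4) | No |
| L-CsA, stops for the same reason and leaves the study | No | Yes | Yes |
| SoC, attends to Week 48 | Yes (SoC runs to study end, SAP 15.2.2) | Not needed | Yes |
| SoC, leaves for adverse event or lack of efficacy | No | Yes | Yes |

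Only the first case is excluded, and only L-CsA patients can be in it. A patient who stops L-CsA, stays for a while and later leaves with a listed reason is kept.

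**Possible size.** The plan gives no figure for this group. Inputs:

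- Randomized: 169 (SAP 8.2) at 1:1 (SAP 7.2), so about 169 / 2 = 84.5 per arm.
- Yardsticks: effect 200 mL and SD 350 mL (SAP 8.2). The plan's figure of 50 per group reproduces: a one-sided t-test at 0.025 with 80% power needs 49.05, rounded up to 50.
- Assumed: a fraction f = 5-15% of L-CsA patients stop for these reasons and stay.
- Assumed: their Week 48 change is d = 0-400 mL worse than that of other L-CsA patients.

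If the other L-CsA patients have mean change m, the mean for the whole arm is (1 - f) x m + f x (m - d) = m - f x d. Removing the group leaves m, so the arm mean rises by f x d.

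- Patients removed: 0.05 x 84.5 = 4.2 to 0.15 x 84.5 = 12.7, that is about 4 to 13 in L-CsA and 0 in SoC.
- d = 0: shift 0 mL for any f.
- d = 200 mL: 0.05 x 200 = 10 mL to 0.15 x 200 = 30 mL.
- d = 400 mL: 0.05 x 400 = 20 mL to 0.15 x 400 = 60 mL.

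The range is 0-60 mL, or 0-30% of 200 mL (60 / 200 = 0.30). For scale, with f = 15% the standard error of a simple difference is 350 x sqrt(1/71.8 + 1/84.5) = 56 mL, so the extreme of the range is about one standard error. This is arithmetic on simple means; the mixed model would give a somewhat different figure.

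**The case against.** Five counter-arguments deserve weight.

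- **The form is not shown.** The protocol uses withdrawal both for leaving the study and for leaving the drug (10.3.1 and 10.3.1.1), so the End Of Study form might carry a treatment reason. This stands as a limit on certainty. But Protocol 10.3 attaches the form to patient withdrawal, and SAP 10 and Table 5 keep treatment and study discontinuation apart.
- **Treatment completion has no single definition.** SAP 8.1.2 refers to 15.2.2 for treatment periods, and 15.2.2 also gives a study-treatment duration that runs to study end in both arms. On that reading an L-CsA stopper who stays would count as a completer and nobody would be lost. This is possible but less likely, since the same section ends the L-CsA period at last dose. The ambiguity itself needs closing.
- **SoC might also be discontinued.** Protocol 15.2.2 mentions early discontinuation of both study treatments. No section says how SoC could end while the patient stays, and Protocol 15 lets the final SAP govern.
- **Membership is settled at a blinded data review** (Protocol 10.3.2, SAP 9.2). That gives an opportunity to notice the problem, but the meeting applies the written definition; nothing lets it readmit patients who fail it.
- **Little depends on the PPS.** It is supplementary, and missing-data robustness is examined mainly in SAP 14.2, with further analyses in 14.3.5 and 14.3.6. This stands and limits the importance of the point.

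A reader might go further and infer that the PPS strips out L-CsA treatment failures generally, that it certainly favours L-CsA, or that the trial's conclusion is at risk. The documents do not support these. Patients who leave for adverse event or lack of efficacy stay in the PPS in both arms, as do deaths recorded under the adverse-event reason. Nothing shows that those who stop and stay decline more: someone who stops for cough may have stable FEV1. And the primary analysis uses all randomized patients, with FEV1 after treatment discontinuation included.

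**Conclusion.** The gap is real on the likelier reading of SAP 9.2.4 and should be corrected, at moderate importance. The rule excludes L-CsA patients who stop for an adverse event or lack of efficacy and comply with follow-up, keeps those who stop and leave, and has no SoC counterpart by this route. SoC patients can still leave the PPS in other ways, such as consent withdrawal, loss to follow-up or a major deviation.

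The conclusion rests on two assumptions: that the End Of Study form of a patient followed to Week 48 shows no withdrawal reason, and that completing randomized treatment refers to the L-CsA period in that arm. The direction, in favour of L-CsA, is plausible because lack-of-efficacy stoppers may decline more, but it is not shown. The 0-60 mL range depends wholly on the assumed f and d. The consequence is confined to the supplementary analysis in SAP 14.3.1.

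**What to change.** Amend SAP 9.2.4 in two places.

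1. Take the reason from the study-treatment discontinuation record, with the End Of Study form as second source. Patients who discontinue L-CsA for adverse event or lack of efficacy then stay in the PPS whether or not they remain in follow-up, with all their FEV1 data, provided there is no major deviation.
2. State that, for the L-CsA arm, completing randomized treatment refers to the L-CsA period defined in SAP 15.2.2.

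The data should be available: Protocol 9.4.3 requires the date and reason for discontinuation on the case report form, and SAP 10 already plans to tabulate reasons for not completing treatment. The cost is a sentence or two and one derivation rule, settled before the blinded data review. With the change, the number excluded by this route is zero in both arms. The downside is that the PPS estimate may become slightly less favourable to L-CsA.

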### 9.3 Study Day and Time from Randomization

Study Day 1 is defined to be the day of the randomization visit (visit 1, week 0). Time from randomization (in days) for subsequent visits is defined to be visit date – date of randomization visit +1.

#### 9.4 Visit Windows

Following randomization, the visits are scheduled every 4-8 weeks, but the actual times of the visits may deviate from the scheduled times. With spirometry data, consideration needs to be taken to remove the rejected spirometry assessments for analysis before applying the visit windowing.

To allow for any presentation that summarizes values by visit, visit windows will be defined according to the table below. Measurements (both scheduled and unscheduled) will be allocated to visits (and analyzed) as reported in Table 2.

Table 2: Visit windows.

Nominal Visit	V1	V2	V3	V4	V5	V6	V7	V8	V9/EoT	V10/EoS
Nominal Week	W0	W4	W8	W12	W16	W24	W32	W40	W48	W52
Nominal Day	1	29	57	85	113	169	225	281	337	365
Time (days) from	0	1-42	43-70	71-98	99-140	141-196	197-252	253-308	*309-364	*365-385
Randomization***	U	1-42	43-70	/1-98	99-140	141-190	197-232	233-308	**309-385	. 202-282

\*Patients who do not consent or participate in BT-L-CsA-303-FU (BOSTON-3).

Data collected after 385 days or 364 days (as applicable, as per the table above) will not be used for analyses but will be included in the listings. If there are two or more measurements assigned to a nominal visit, only the one closest to the scheduled time of the visit will be used in the analysis, unless an additional measurement will be the last measurement during a patient's trial participation

Final Version 5.0 Page 29 of 76

\*\*Patients who consented and participated in BT-L-CsA-303-FU (BOSTON-3) and will not have a V10 / EoS

\*\*\* Visit windows are based on [visit date – date of randomization visit] formula for time (days) from randomization.

(e.g., in case of an unscheduled visit before premature withdrawal), which will always be included into the analysis.

In the case a scheduled visit is performed in the same date of an unscheduled visit, the scheduled visit assessments will be used; in the specific case of spirometries, if the spirometry data is accepted in the scheduled visit, the scheduled visit data will be used, otherwise (if the spirometry in the scheduled visit is rejected) if the spirometry data is accepted in the unscheduled visit, the unscheduled visit data will be used.

Finally, if a nominal visit has more than one accepted spirometry data assigned, and some of them are performed after IMP inhalation, then only the spirometries done before inhaling the IMP will be used for the visit window mapping rules described above. Instead, if all the accepted spirometries of the nominal visit are done after inhaling the IMP, then all of them will be considered for the above mapping rules. Spirometries collected at 1h and 4h post dose will be used only for safety evaluations and will only be presented in data listings.

Windowing will be applied to the data prior to any missing data imputation.

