#### 14.2.7 Unscheduled Visits

Whenever medically warranted, the Investigator may ask the patient to appear or the patient may elect to appear at the clinic for an unscheduled visit. All medical measures performed as appropriate shall be documented in the Case Report Form for unscheduled visits.

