### 14.1.3 Analysis Model

The primary efficacy analysis will be carried out using a LMM for repeated measurements, using all observed available  $FEV_1$  measurements. In case of death or re-transplantation events,  $FEV_1$  will be imputed as zero at each nominal day post event.

The dependent variables are the absolute change from baseline of FEV1 measurements at visit 2 (i.e., the first post-baseline visit) through visit 9 (Week 48). For the definition of baseline FEV1 please refer to section 8.1.1.

A flexible and robust model will be chosen for the random part of the LMM according to a prespecified stepwise procedure (see next section). The fixed part of the LMM is specified as follows: the model will contain (except from the intercept) time cubic splines, treatment, the interactions of time splines by treatment, baseline FEV1, the interactions of time splines with the baseline FEV1, region (North America versus all other countries together), age (< 55 versus  $\ge 55$  years), and use of azithromycin at randomization (i.e. Baseline, Visit 1).

The primary efficacy parameter will be estimated from the model by the adjusted difference between treatment groups in mean FEV1 change from baseline after 48 weeks. The p-value for the null hypothesis of no difference and a two-sided 95% confidence interval for the difference will be provided.

Superiority of L-CsA will be demonstrated by a statistically significant result (defined as p<0.025, one-sided) in favor of the L-CsA plus SoC treatment compared to SoC alone.

The above comparison between treatment groups at all the other visits (2-8) will also be presented.

A figure of observed mean change from baseline and standard errors at each visit, by treatment group will be presented. A figure with adjusted mean changes from baseline at each visit by treatment group derived from the LMM will be provided.

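### SAP 9.4 lets a medically triggered unscheduled FEV1 reading displace an accepted scheduled one that lies further from the nominal day; a scheduled-first rule would prevent this at little cost

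*SAP*

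**What the plan says.** SAP 9.4 treats the two kinds of reading alike: "Measurements (both scheduled and unscheduled) will be allocated to visits (and analyzed) as reported in Table 2". Where a window receives two or more, "only the one closest to the scheduled time of the visit will be used in the analysis". The SAP modifies this in four ways:

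- Rejected spirometries are removed before windowing.
- Where some accepted readings in a window follow inhalation of study drug, "then only the spirometries done before inhaling the IMP will be used for the visit window mapping rules described above".
- On a shared date the scheduled visit has priority: "In the case a scheduled visit is performed in the same date of an unscheduled visit, the scheduled visit assessments will be used". If its spirometry was rejected, an accepted unscheduled one from that date is used.
- A patient's last measurement in the trial is one "which will always be included into the analysis", with an unscheduled visit before withdrawal as the example.

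None of these protects an accepted scheduled reading from an accepted unscheduled one on a different date.

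Protocol 14.2.7 gives the reason for unscheduled visits: "Whenever medically warranted, the Investigator may ask the patient to appear or the patient may elect to appear at the clinic". SAP 7.2 confirms that treating physicians, site staff and patients know the treatment assignment.

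For the primary model, SAP 14.1.3 says the analysis will be "carried out using a LMM for repeated measurements, using all observed available" FEV1 measurements, with change from baseline at visits 2 to 9 as the outcome.

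**The concern.** Scheduled visits are fixed by design. Unscheduled ones happen because of the patient's condition or wishes. If the two compete on closeness to the nominal day, how the patient is doing partly decides which value represents a visit. The blinded technicians and the blinded central over-read protect how FEV1 is measured, not when or why.

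The decision to attend is made by people who know the arm. Some reasons for an extra visit exist only under L-CsA, for example suspected intolerance of the inhaled drug (Protocol 9.4.3). If the arms differ in how often such readings occur, and those readings run lower, part of the observed FEV1 difference would come from the selection rule even though an accepted scheduled reading is in the database.

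**Working it through.** **Plan's own figure.** The SAP gives no figure for displacement. The yardstick available is the design effect in SAP 8.2: 200 mL, SD 350 mL, one-sided alpha 0.025, at least 80% power with 50 per arm. This reproduces. The noncentral t gives 79.96% power at 49 per arm and 80.8% at 50. Nothing below changes it.

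**Worked case, V7.** Table 2 gives nominal day 225. Its footnote counts days without adding one, which makes the nominal day 224. The protocol allows 14 days either side. A scheduled reading on day 234 is 9 or 10 days off, depending on the day count. An unscheduled reading on day 220 is 5 or 4 days off. Under either count the SAP keeps the unscheduled reading and drops the accepted scheduled one.

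**How often.** Assume that a window holds one accepted reading of each type on different dates, that the scheduled date is uniform over the protocol window of w days either side, and that the unscheduled date is uniform over the SAP window of L days. Then:

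- Possible date pairs: (2w + 1)(L - 1).
- A scheduled reading d days off nominal loses to 2d - 1 dates, and two scheduled dates share each d. Pairs lost: sum over d = 1 to w of 2(2d - 1) = 2w².
- Displacement probability: p = 2w² / [(2w + 1)(L - 1)].
- Ties, for which the SAP has no rule: 2w / [(2w + 1)(L - 1)].

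| Visit | w (Protocol 14) | L (SAP Table 2) | p | Ties |
|---|---|---|---|---|
| V2, V5 | 7 | 42 | 98/615 = 15.9% | 14/615 = 2.3% |
| V3, V4 | 7 | 28 | 98/405 = 24.2% | 14/405 = 3.5% |
| V6-V8, V9 without rollover | 14 | 56 | 392/1595 = 24.6% | 28/1595 = 1.8% |
| V9 with rollover to BOSTON-3 | 14 | 77 | 392/2204 = 17.8% | 28/2204 = 1.3% |

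The V9 figures are before the last-measurement clause is applied.

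**Size at an affected visit.** Bias = p × (arm difference in the share of windows with an unscheduled reading) × (mean FEV1 deficit of that reading), taking p and the deficit as equal in both arms. The documents give neither of the last two terms. Assumed ranges are 10-30 percentage points and 150-300 mL:

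- Low end: 0.159 × 0.10 × 150 = 2.4 mL.
- High end: 0.246 × 0.30 × 300 = 22.1 mL.
- With no arm difference the product is zero, but noise is still added.

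**Which analyses it reaches.**

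- MMRM (SAP 14.2.3) uses categorical scheduled visits, and ANCOVA (14.2.5) and the t-test (14.3.4) use change to Week 48. These and the by-visit tables need one value per visit, so 9.4 applies.
- For the primary mixed model the text points both ways. SAP 9.4 introduces windows for by-visit presentation, 14.1.3 takes all available FEV1, and 14.1.5 uses actual visit times. Against that, 9.4 also says that windowed measurements are analyzed, 14.1.3 defines the outcome at visits 2 to 9, and 14.2.1 applies the 9.4 remapping before fitting the same model.

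**The case against.** The rule is pre-specified and arm-neutral on its face, and several counter-arguments stand at least in part.

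- **Primary model.** A reader might infer that 9.4 definitely replaces readings in the primary model and so contradicts 14.1.3. The documents do not settle this. If the model truly takes every available reading, nothing is replaced and unscheduled readings enter as additions. If 9.4 defines the input, all available readings can mean those left after windowing, and there is no contradiction. What stands is an ambiguity that needs one sentence.
- **Week 48.** For patients entering BOSTON-3, V9 is the end-of-study visit, so the scheduled V9 reading is normally their last and is kept. Displacement at V9 then mainly concerns patients who do not roll over, whose number is not given. The clause also does not say whether the last reading replaces the closest one or is added to it.
- **Confirmation of BOS progression.** Confirmatory readings must be at least two weeks apart (Protocol 12.1.2). At V2-V5, with the scheduled visit within 7 days of nominal, a reading 14 or more days away cannot be strictly closer. At V6-V9 it can win only if the scheduled visit is more than 7 days off. The uniform-date assumption ignores this, so confirmation visits are a weaker route than illness visits.
- **Arm dependence.** It is possible, not shown. Protocol 14.2.7 does not require spirometry at unscheduled visits, and Protocol 7.1.3 and 7.1.4 report no increased risk of respiratory infection with L-CsA. A 30-point arm difference would need at least 30% of windows in one arm to hold an unscheduled reading, so the upper end of the range is demanding.
- **Post-event readings are legitimate.** The estimand uses FEV1 after most intercurrent events, and scheduled dates can move too. The weakness is not that readings taken during illness are used, but that the reason for an extra visit can decide which of two accepted values counts.

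**Conclusion.** The concern holds as a weakness in the selection rule, one that should be corrected because it is cheap to correct. When one reading of each type falls in a window on different dates, an accepted scheduled value is displaced in about 16-25% of cases (18% at V9 with rollover, before the last-measurement clause). This rests on uniform dates.

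The effect on the treatment comparison cannot be determined from the documents. The 2-22 mL range applies to a single affected visit and rests wholly on assumed deficits and arm differences. Its direction depends on which arm has more unscheduled readings, and there is no systematic bias if the arms do not differ.

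A reader might be tempted to set this range against the 200 mL design effect and conclude that the primary result is biased by up to about a tenth. That does not follow. The 200 mL is a Week 48 difference, no Week 48 bias in the mixed model has been derived, the model dilutes a single-visit shift across visits, and the scheduled V9 reading is usually retained for rollover patients.

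**What to change.** Amend SAP 9.4 as follows:

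1. Within a window, use the accepted scheduled-visit reading, identified by its CRF visit label, whenever one exists. Use the closest accepted unscheduled reading only when none exists.
2. For two scheduled-labelled readings in one window, or for ties, take the closest and then the earlier.
3. State that the last-measurement clause does not let an unscheduled reading replace an accepted scheduled one in analyses that use one value per visit.
4. State whether 9.4 governs the data entering the primary mixed model.

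This extends the SAP's own same-date preference to the whole window and reduces displacement of an accepted scheduled reading by an unscheduled one to zero. Unscheduled readings would still be used where the scheduled one is missing or rejected.

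The cost is a few sentences in the SAP and a sort key in the derivation program. Some values will lie a few days further from the nominal day, which the mixed model handles because it uses actual visit times. The change belongs in an updated SAP before database lock and before any comparative results are seen, the condition recorded in SAP 8.3.4.
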